## Enrollment

Potential participants will be considered to be enrolled in the study upon meeting eligibility criteria, completion of written informed consent, satisfactory completion of screening laboratory tests. No data, except that which is necessary for scheduling will be collected prior to informed consent.

## Laboratory Specimens and Evaluations

During the course of this study, clinical laboratory specimens will be collected for research purposes. In order to determine eligibility for study participation, the subject will be consented and a screening lab test will be performed to make a diagnostic determination regarding GWI status and to evaluate the presence or absence of exclusionary medical conditions. For the virtual platform, the Miami VA research team will ship collection boxes directly to the participant. Samples will be drawn and packed by phlebotomists at Quest Laboratories in the participant's local area and shipped via overnight express for analysis at the Miami VAMC. The health assessment also will consist of a medical history, physical examination, and laboratory testing listed in Table 1.

**Protocol for Blood Samples.** At each of the clinical sites, blood samples will be obtained from each subject for the tests shown in Table 1 as well as the study sample storage for batched assays.

Appropriate samples for CBC, CMP, and U/A are sent to the Miami Lab. Whole blood samples are collected from the patients, according to the outline shown in Table 3. The blood samples are to be collected in afternoon and shipped by overnight carrier to the lab at the Miami VA Medical Center. Salivary samples will be collected 4 times over 24 hours and stored frozen at the sites, to be shipped on dry ice in batches to Miami VA.

## Table 3. Blood Samples each onsite visit

	Serum	Plasma	PBMC
Tubes	one 10 ml red top	two 7 ml purple top	four10 ml green
Total: 64 ml	(siliconized)	EDTA	tops (sodium

## Types of samples and storage requirements

- 1. Peripheral blood mononuclear cells are separated from blood and cryopreserved according required protocol. Viability and cell count is determined and aliquots are placed in freezer vials and stored in liquid nitrogen or at -80°C as required by protocol.
- 2. Plasma is separated from the cellular component of blood by centrifugation and stored in required aliquots at -80°C.
- 3. Serum is separated from the clot by centrifugation and stored in required aliquots at -40°C.

**Monitoring of freezers** All mechanical freezers are connected to emergency outlets. If a freezer goes down, an alarm goes off in the building engineering section and lab personnel are immediately notified. In addition, the lab personnel check the interior temperature each day and record it on a chart attached to the freezer door. If the building power is disrupted, the freezers are automatically connected to the emergency generator system. Liquid nitrogen freezers are checked each day. The level of liquid nitrogen is measured and adjusted if needed. A liquid nitrogen storage tank is available in the freezer room. The storage tank is replaced each month.

## Laboratory Measurements (Measured at T0, 16w, and T24 w)

1. **CoQ10 in plasma:** The method of Tang and Miles (2012) will be used to measure reduced (ubiquinol) and oxidized (ubiquinone) CoQ10. Plasma is extracted with 1-propanol. After centrifugation, the 1-propanol supernatant is directly injected into HPLC and monitored at a dual-

electrode. This method meets regulatory requirements for clinical laboratories, and has been proven reliable for analysis of clinical and research samples for clinical trials. CoQ10 screening will take place at the 8 week visit.

**2. Hormone studies: Hypothalamic-pituitary-thyroid (HPT) axis.** Thyroid status is assessed using a chemiluminescent method (TSH, free T3, free T4), Hypothalamic Pituitary Gonadal axis will be measured using ELISA methods measuring testosterone (free), FSH, LH and estrogen. Cortisol will be measured using a 24 hour salivary collection with 4 time points to assess circadian rhythm. The measures will be evaluated at baseline and to evaluate response to treatment.

**3.Safety and screening labs**: CBC, CMP and urinalysis will be performed at every time point as a safety screen: HIV, Hep B, C, Rheumatoid factor, Antinuclear antibody, CBC, CRP, and HbA1c, and LFTS will be drawn at screening to rule out exclusionary illnesses.

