
Laboratory Variables	Screening on-site	T0 on-site	4 wk on-line	8 wk on-site	12 wk on-line	16 wk on-site	20 wk on-line	24 wk on-site	28 wk on- line
CBC with diff		Ø		Ø		$\odot$		Ø	
CMP	Ø	Ø	1			Ø		Ø	
U/A	Ø	Ø				Ø		Ø	
Cortisol series		Ø		Ø		Ø		Ø	
Autonomic measures		Ø				Ø		Ø	
HPG axis		Ø				Ø		Ø	
HPT axis		Ø				Ø		Ø	
CoQ10		Ø		Ø		Ø		Ø	
Exclusion HIV, Hep B, C, RA, CBC, RF, LFTS, CRP, HbA1c	Ø								
Stored sample for biomarker studies	Ø	Ø		Ø		Ø		Ø	

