#### Selection of CoQ10 product study medication and composition of placebo

The decision to use the reduced form of CoQ10 (ubiquinol) over the oxidized form (ubiquinone) was based on the following factors: (1) Ubiquinol accounts for approximately 95% of the total CoQ10 plasma concentration; (2) Ubiquinol is responsible for the antioxidant activity in the mitochondria and lipid membranes; (3) Ubiquinol has a higher oral bioavailability than ubiquinone resulting in higher plasma concentrations. The active formulation will be soft gelatin capsules containing 200 mg of CoQ10 (ubiquinol) emulsified with diglycerol monooleate, rapeseed oil, soy lecithin, and beeswax and the matching placebo formulation will be soft gelatin capsules containing all the above ingredients excluding CoQ10. We will be administering one 400 mg ubiquinol capsules for 2 months followed by 200 mg per day for the remaining 4 months of the clinical trial. The active and placebo soft gelatin capsules will I be provided by Kaneka Nutrients, an FDA registered, NSF International and Natural Products Association (NPA) Good Manufacturing Practices (GMP) certified facility that manufactures United States Pharmacopeia (USP) compliant supplements. The purity and stability of the CoQ10 soft gelatin capsules will be monitored by the VA CSP CRPCC Laboratory following USP standards.

**Pre-Enrollment Screening**: Case definition: In our prior work and in [name]'s work using CoQ10 in GWI, we have used concurrent CDC and Kansas case definitions (Steele, 2000; Fukuda et al., 1998). The more rigorous Kansas case definition captures at least a third of the deployed veterans from the first Gulf War (Research Advisory Committee Report, 2014, page 18), and the CDC captures about 10% more. The key difference between the two is the factor analysis based Kansas definition weighted severity and frequency of symptoms. The Kansas definition requires deployment to the theater of operations between August 8, 1990 and July 31, 1991 with multiple and moderately severe symptoms (> 6 months) in at least 3 of 6 symptom domains; excluding serious medical/psychiatric diagnoses that account for symptoms or preclude accurate symptom reporting. The 6 domains are fatigue/sleep problems; somatic pain symptoms; neuro/cognitive/mood symptoms; gastrointestinal symptoms; respiratory symptoms, and skin symptoms. The exclusion criteria as modified by Steele in 2014 allow for common comorbid conditions.

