
The clinical and laboratory testing is performed without knowledge of the subjects' group membership, the group A vs B true condition will remain blinded throughout the study until its conclusion. There are two treatment conditions: CoQ10 (ubiquinol) 400mg for 2 months followed

by 200mg maintenance for 4 months and placebo taken once a day in the morning with food. The subject schedule includes 5 on-site assessments. On-site assessments include the screening visit with informed consent, the drug initiation visit, an 8 week visit and the 16 and 24-week visits. In addition, there is a web based self-report assessment given every 4 weeks throughout the treatment period and at 4 weeks after completion of the study drug. A member of the research team may contact the participant by phone to remind him or her to complete the surveys on the computer. Subjects will also utilize an activity monitor (FitBit) device to assess activity and sleep throughout the study period through 7 months. **(Assessments, see Table 1.)** 

The CSR&D Data Monitoring Committee (DMC) and the local VA pharmacist will have the authority to break the blind and recommend stopping the study should one group have evidence of adverse effects or significant efficacy in group A or B that would ethically require the blind to be broken. Further details regarding the interim efficacy analysis and formal efficacy stopping rules are provided in the statistical section below. There will be no formal stopping rules for safety; the DMC may recommend stopping the study for any concerns they feel jeopardize the safety of patients in the trial regardless of resulting p-values. The research pharmacist will also have access to an electronic emergency unblinding system developed by the CSP Pharmacy Center should an individual subject event require the blind be broken to access appropriate care (e.g., a toxic reaction to a product requiring treatment). This decision would follow institutional guidelines, following a discussion with the treating clinician. All subjects will have a physical examination, medical history, and will be given a battery of psychometric questionnaires.

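### Table 1 shows no clear chemistry (CMP) or urinalysis mark at week 8, the only post-dose on-site visit tied to 400 mg/day, although the text promises both as a routine safety screen

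*Combined protocol and SAP*

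**What the plan says.** Item 3 of *Laboratory Measurements* (safety and screening labs) states: "CBC, CMP and urinalysis will be performed at every time point as a safety screen". The section's own heading gives a narrower list: "Laboratory Measurements (Measured at T0, 16w, and T24 w". Yet item 1 of the same section adds a further visit for one assay: "CoQ10 screening will take place at the 8 week visit".

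Under *Entry Criteria*, "The subject schedule includes 5 on-site assessments": screening, drug initiation (T0), and weeks 8, 16 and 24. The other scheduled contacts (weeks 4, 12, 20 and 28) are on-line. Dosing, in the section on selecting the product, is "400 mg ubiquinol capsules for 2 months followed by 200 mg per day for the remaining 4 months".

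The laboratory part of Table 1 marks CBC, the cortisol series, CoQ10 and a stored sample at week 8. It leaves week 8 empty for CMP and U/A. At screening, CBC is covered by a separate row: "Exclusion HIV, Hep B, C, RA, CBC, RF, LFTS, CRP, HbA1c".

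Two places point the reader to Table 1 as the schedule. The visit description under *Entry Criteria* refers to it for assessments. *Laboratory Specimens and Evaluations* refers to it for laboratory testing in general and again for blood: "blood samples will be obtained from each subject for the tests shown in Table 1". That section also handles the three safety tests together: "Appropriate samples for CBC, CMP, and U/A are sent to the Miami Lab".

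**The concern.** One sentence treats CBC, CMP and urinalysis alike, while the table separates them at a single visit. That visit is the only on-site one after dosing starts that is tied to 400 mg/day.

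*Safety and Tolerability and Dosage*, repeated in the risk section, says that asymptomatic LDH and hepatic-enzyme elevations may occur above 300 mg/day of CoQ10. A symptom-free rise is not something a participant would report as an adverse event; scheduled chemistry is how it would be found. If no chemistry is drawn at the peak dose, a rise that appears during loading and settles after the step-down leaves no trace in the data. The by-visit laboratory summaries under *Safety Endpoints* would then describe baseline and maintenance only.

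**Working it through.** No sample-size or alpha calculation is involved. The check is a cell-by-cell reading of Table 1 against the visit and dose schedule.

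**Marks in Table 1** (the 12, 20 and 28 wk columns are empty for all these rows):

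| Row | Screening | T0 | 4 wk | 8 wk | 16 wk | 24 wk |
|---|---|---|---|---|---|---|
| CBC | yes (exclusion row) | yes | – | yes | yes | yes |
| CMP | yes | yes | '1' | – | yes | yes |
| U/A | yes | yes | – | – | yes | yes |
| Cortisol, CoQ10 | – | yes | – | yes | yes | yes |
| HPG and HPT axes | – | yes | – | – | yes | yes |
| Stored sample | yes | yes | – | yes | yes | yes |

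**Counts.** On-site visits with the test marked: CBC 5 of 5; CMP 4 of 5; U/A 4 of 5. Post-dose on-site visits with CMP and U/A marked: 0 of 1 tied to 400 mg/day, and 2 of 2 at 200 mg/day.

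**Timing.** The first on-treatment panel is at week 16: 16 × 7 = day 112. Treatment lasts 24 × 7 = 168 days, and 112/168 = 66.7%. The gaps are 16 weeks (T0 to week 16) and 8 weeks (week 16 to week 24). With week 8 added, they are 8, 8 and 8 weeks.

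**Length of the loading phase.** The plan says 2 months. Taking that as 56 to 62 days (an assumption), the phase is 56/168 = 33.3% to 62/168 = 36.9% of treatment. The week 16 panel then falls 112 − 62 = 50 to 112 − 56 = 56 days after the step-down.

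**Dose against the 300 mg/day threshold.** The protocol equates 200 mg of ubiquinol with 600 mg of ubiquinone, a ratio of 3. It does not say which form the threshold refers to.
- If ubiquinol: loading (400 mg) is above 300 and maintenance (200 mg) is below.
- If ubiquinone: maintenance corresponds to 600 mg and loading, at the same ratio, to 400 × 3 = 1,200 mg. Both are above 300.

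On either reading, loading is the higher exposure and has no scheduled chemistry.

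**The stray '1'.** It stands in the CMP row under week 4, an on-line visit, next to the empty week 8 cell. If it is a displaced week 8 mark, the CMP gap is already 8 weeks and only urinalysis is missing. The U/A row has no such mark, and the week 8 marks in other rows are intact, so general loss of that column is unlikely.

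**Feasibility.** Table 3 draws 10 + 2 × 7 + 4 × 10 = 64 ml at each on-site visit. The cap under *Screening labs* is 120 ml, which leaves 120 − 64 = 56 ml.

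**The case against.** The strongest reply is that text and table agree. *Every time point* cannot be literal, since four contacts are on-line. The section heading supplies T0, week 16 and week 24, and the CMP and U/A rows show those visits plus screening, the same post-baseline pattern as the two hormone-axis rows. This has force: for these two tests the conflict may be no more than loose wording. It does not explain why CBC, in the same sentence, is marked at week 8. On this reading, too, no chemistry is drawn at 400 mg/day.

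Second, the safety rationale rests on CMP, which has the less reliable blank; the documents describe no urinary safety signal. That stands, and it is why the original table must be checked first.

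Third, the signal is mild. The sentence that mentions enzyme rises goes on to say that serious hepatotoxicity has not been reported. If the threshold refers to ubiquinone, the week 16 and 24 panels already monitor exposure above it. Both points stand and limit the severity.

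Fourth, week 8 is not unmonitored: CBC, CoQ10 and a stored sample are taken, on-site participants have a brief examination, and adverse-event reporting and DMC oversight continue. None of these replaces timely chemistry.

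Stronger readings are tempting, but the documents do not support them:
- A reader might infer that Table 1 governs blood only, so that it is open which text controls urinalysis. *Laboratory Specimens and Evaluations* also refers to the table for laboratory testing without that limit.
- A reader might infer that sites will diverge and leave a partial week 8 data set. Analysis is centralised in Miami, and nothing shows that collection will differ by site.
- A reader might infer that hepatic effects of the drug go unmonitored. Panels at weeks 16 and 24 are marked clearly.

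**Conclusion.** The point holds as a minor one. As the table reads, a site following it draws no scheduled CMP or urinalysis for 16 weeks from T0, and none in the 400 mg/day phase (33% to 37% of treatment). What could be lost is limited to rises that appear and resolve during loading. The primary endpoint, power and alpha are not touched.

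The conclusion assumes that Table 1 is the operative schedule, that the '1' in the CMP row is not a week 8 mark, that 2 months means 56 to 62 days, and that CMP includes hepatic enzymes (the protocol does not list its analytes or say whether LDH is among them). If the '1' proves to be a week 8 mark, only the urinalysis gap and the wording remain.

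**What to change.** 1. Check the CMP row against the original table.
2. Mark CMP and U/A in the 8 wk column of Table 1, and state that the samples are taken before the step-down to 200 mg.
3. Add week 8 to the heading of *Laboratory Measurements*.
4. In item 3, replace *every time point* with: screening, T0, weeks 8, 16 and 24.

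The cost is at most 4 sites × 50 participants = about 200 extra chemistry panels and 200 urine samples. No new visit or venipuncture is needed. Virtual participants have blood drawn at an outside laboratory and no urine procedure is described for them, so week 8 urine would have to be arranged, as it already must be at the other visits.

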## Laboratories Performing Evaluations

The clinical laboratories under the direction of [name] [name] and [name] at the Miami VA will be used for medical laboratory testing. Local VA laboratories will pack, and ship blood and saliva tests and will discard any residual samples. All research specimens will be processed at the Miami VA.

## Laboratory Storage

Biological samples and laboratory data will be stored at the Miami VA Healthcare System, (Miami, FL) and related clinical data will be stored on a secure server. All samples will be processed and maintained according to documented SOPs that follow generally accepted good laboratory practices in order to assure sample quality, integrity and long-term stability.

All clinical data for consenting subjects will be stored indefinitely under conditions protecting PHI. In the event that a subject withdraws consent, [name] will be informed of their Subject ID and their clinical information will be expunded from the database, and biological samples will be destroyed.

## Data Analysis Plan

## Statistical considerations

**General Statistical Approach:** Patients will be randomized in a 1:1 manner to Coq10 or placebo; randomization will be stratified by study center and gender. This study includes a comprehensive survey of patient status using a broad set of clinical assessments and laboratory assays designed to assess the response to treatment Unless otherwise specified, two-sided P < 0.05 will be considered statistically significant. Statistical analyses will be carried out using SAS Version 9.4 or higher.

**a) Baseline:** Differences in continuous baseline variables will be compared by a two-sample t test. The Mann-Whitney U test will be used in the case of non-normal distribution. For baseline categorical variables, Fisher's exact test will be used.

**b)** Evaluating the efficacy of CoQ10 in GWI: The primary analysis is to compare treatment groups on change from baseline SF-36 physical function score over time (6 monthly time points from Week 4 to Week 24) in a repeated measures setting using a final two-sided 0.049 level of significance (a 0.049 level is being used at the end of the study instead of 0.05 to account for the interim analysis further described below). This will be carried out using a mixed model (MM) analysis of variance (ANOVA) with effects for treatment, time, baseline physical function score and the randomization strata of study center and gender. The within-patient correlation structure will be assumed to be unstructured. If this analysis shows a significant treatment difference across time or a significant treatment-by-time interaction, comparisons across treatment (significance level at each time point using a Bonferroni alpha-adjustment (significance level at each time point = 0.049 divided by 6, the number of planned post-baseline time points) to account for the multiple comparisons. Data will be analyzed as an intention-to-treat model; i.e., all

randomized subjects will be included using available data (i.e., a patient does not have to provide data through the end of the study to be included in the analysis; this is the strength of the MM ANOVA approach). A secondary supportive analyses will be carried out where missing physical function data at each time point are first imputed via monotone multiple linear regression imputation, under the assumption the missing data mechanism is missing at random prior to carrying out the mixed model analysis. The imputation regression model at each time point will include randomized treatment, measures of the primary outcome at earlier time points and baseline covariates that will be specified in the final detailed statistical plan. Fifty imputed datasets will be created, and the MM ANOVA will be run on each data set; the 50 MM ANOVA results will then be combined across the data sets using PROC MIANALYZE in SAS to obtain one overall assessment of treatment difference on the imputed data.

**c) Sample size justification and power analysis:** In this study population, we rely on the literature of Phase III studies of other inflammatory states to determine assumptions required for sample size calculations. Our primary clinical outcome variable is physical function of the SF36 measured over time (approximately monthly from week 4 through week 24; i.e., 6 measurements over time). Our current data suggests a coefficient of variation (CV) of approximately 0.40 for physical function at a given time point. Assuming this and assuming a relative increase in SF36 of at least 21% for Coq10 over placebo at each time point, then there is a 0.525 treatment effect size at each time point. Under this effect size, power is at least 95% to detect a treatment difference over time using an evaluable group sample size of n=90 subjects at a two-sided 0.049 level of significance regardless of the within- patient correlation between time points. To account for approximately 10% attrition, 100 subjects per group will be randomized. Such an evaluable sample size will also allow at least 80% power to detect a relative increase t of 21% separately at each time point after using a Bonferroni multiple comparison adjustment across the six time points.

**d)** Subgroup analysis on the primary endpoint: Treatments will be compared within each gender. The purpose of this analysis is not to show a statistically significant Coq10 effect on the primary endpoint within each gender (due to potential lack of power; e.g., if there are 25 evaluable women in each treatment group, power ranges from approximately 50% to 95% depending on the within-patient correlation between time points under the effect size assumptions used in the primary power calculation), but rather to investigate consistency of treatment difference across genders. In addition, treatment-by-gender interaction will be assessed in a mixed model repeated measures model that includes the main effects in the primary analysis and a term for treatment-by-gender interaction; an interaction p-value <0.15 will be considered as possibility indicating lack of consistency in treatment effect across gender. Similar analyses will be conducted to assess consistency of results across study centers.

e)Other clinical efficacy end points will look at each of the self-report assessment measures across the domains of fatigue, pain, sleep, and the SF36 subscales of function and severity. Objective measures include laboratory data that could reasonably be considered a surrogate for illness severity (e.g., measures of immune activation, inflammation, cell function, and NPY), a focus of several of our prior publications ([name] 2002, 2009, 2010; Maher 2007; Broderick 2009, 2010). Other objective measures include cognitive assessments and the activity monitor data which will be measured at each assessment point at the beginning of the study and on the 24th week of treatment. These will all be analyzed in a similar manner as the primary endpoint. We will also look at the effect of duration of study drug exposure on a case by case basis if there are individuals who fail to complete 24 weeks of study drug, and will also look at the change in CoQ10 levels as a predictor of response. These endpoints are considered exploratory and no adjustment of significance level for the multiple comparisons will be applied.

**f) Safety Endpoints:** The primary safety variable is the incidence of treatment emergent adverse events (TEAEs). A TEAE is an event that emerges, or a pre-existing event that worsens, any time after initiation of first study treatment. Adverse events will be coded by using the most recent released version of MedDRA at the time of study start. The incidence of TEAEs will be presented overall and by MedDRA system organ class and preferred term. TEAEs will also be presented by

severity (mild, moderate, or severe). Patients experiencing more than one occurrence of the same preferred term or system organ class will be categorized under the maximum severity experienced for that preferred term or system organ class. Similar analyses of TEAEs will be conducted by relationship to drug. Patients experiencing more than one occurrence of the same preferred term or system organ class. This will be repeated for serious TEAEs. Descriptive statistics (sample size, mean and median, quartiles, minimum and maximum) of laboratory values will be presented for each visit in which they were collected. Similarly, descriptive statistics from the change from baseline to each visit will be presented. Box plots of the changes from baseline will be presented across visits.

g) Evaluation of blinding: Each subject and investigator will be asked at the end of their follow-up to guess whether they believe the subject was randomized to active treatment or sham group. Frequencies of correct and incorrect responses will be provided separately for subjects and for investigators.

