## **Gulf War Registry recruitment**

It is critical that the recruitment projected in this study be on timeline, in order to complete the study in the 3 year timeframe. Prior clinical trials studies have suffered from difficulties with recruitment, often because the per site recruitment targets were ambitious, access to the study population limited, or studies were understaffed. For that reason, we have paid attention to all of these issues, performing this study across 4 sites with established track records of successful recruitment. In addition, we have included a national recruiter working from the national and regional registry, contacting potential subjects and performing scripted screening interviews to refer to the study. A similar strategy was recently employed by the Synergy trial, fully recruiting and completing a similarly powered (number of subjects)/number of sites study in just 18 months. Thus, the study population will be drawn from established GWI populations from 4 VAs with a track record of successful recruitment for clinical studies.

The PI, [name], will seek a DUA to access the national Gulf War Registry list. After gaining access, the Registry Recruiter will mail an introductory letter to the GW veteran. Upon response, the Registry Recruiter will call the veteran by telephone to discuss the study eligibility and then will mail eligible veterans a study packet containing information about the study and directions to the study site. The Registry Recruiter will coordinate scheduling an appointment and travel arrangements, if necessary. After reporting to the clinic site, veterans will be asked for consent to participate, after being fully informed about the study, including risks and human subjects' protections.

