## Data and Safety Monitoring Plan

#### **Risk management and Emergency Response:**

This study has been assigned for administrative and scientific oversight to the Clinical Services Research and Development Data Monitoring Committee (DMC) to [name] and his staff based at the Hines VAMC. They will monitor the study for safety, efficacy, and progress. Study participants will be asked to self-monitor and report to study personnel any episodes of symptoms. Adverse reactions will be reported to the Project Manager ([name]) who will communicate with [name], the local IRB, and the DMC. While other trials have not seen serious adverse reactions, standard protocols are in place, with moderate to severe reactions r e p or t ed to both the IRB and the DMC All unanticipated problems involving risk to subjects or others, serious adverse events, and all subject deaths associated with the protocol will be reported. Comments will be recorded on the outcomes of the event or problem. In the case of a serious adverse event, an assessment will be made on the relationship to the participation in the study. All reports determined by the investigators or DMC to be possibly or definitely related to study participation and reports of events resulting in serious adverse events will be promptly forwarded to the VACO ORD.

Should a systemic allergic reaction occur, subjects are advised to call 911, and take an antihistamine while awaiting response. The most common complaint with ubiquinol is GI upset and diarrhea. This is handled by taking the medication with food and if necessary with dose adjustment to 50%. All of the VA medical centers have a VA Emergency room that is available 24/7 if for some reason the study physician or back up is not available.

Veterans are the study population and are cared for by the VA health care system, which will assume the costs of study related injuries. Women of childbearing years are asked to take measures to avoid pregnancy during the study. Barrier methods or better are sufficient.

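### Does the missing interim stopping rule make the 0.049 final significance level unsound?

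*Combined protocol and SAP*

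**What the plan says.** The paragraph on blinding and the Data Monitoring Committee (DMC), under Entry Criteria, states: "Further details regarding the interim efficacy analysis and formal efficacy stopping rules are provided in the statistical section below". It adds that there is no formal rule for safety, so the promised rule concerns efficacy. The Data Analysis Plan, item b), then sets the final two-sided level at 0.049 and gives the reason: "a 0.049 level is being used at the end of the study instead of 0.05 to account for the interim analysis further described below".

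Items a) to g) follow without a skipped letter, and the Data and Safety Monitoring Plan comes after them. Neither describes an interim efficacy analysis. One further document is mentioned, in the imputation text of item b), which refers to "baseline covariates that will be specified in the final detailed statistical plan". It was not supplied, and it is cited there only for those covariates.

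On oversight, the Entry Criteria paragraph says the "Data Monitoring Committee (DMC) and the local VA pharmacist will have the authority to break the blind and recommend stopping the study". The Data and Safety Monitoring Plan says of the DMC and its staff: "They will monitor the study for safety, efficacy, and progress". The separate Monitoring Plan makes the investigators and research staff responsible for data safety.

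**The concern.** A stopping rule protects the type I error only if it is fixed before unblinded results are seen. Here it is promised twice and not found, so a reader cannot tell from this document when the trial could stop or at what p-value.

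Three further worries follow.

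- A final level of 0.049 does not identify the rule, because more than one boundary is compatible with it.
- Under a spending function, the correct final level depends on the information at the look. The primary model uses incomplete follow-up ("a patient does not have to provide data through the end of the study to be included in the analysis"). If the interim did the same, a look triggered by a count of completers would fall later in information than the count suggests, and 0.049 would be slightly too generous.
- The endpoint is self-reported, so knowledge of unblinded group results outside the DMC could bias later responses, and three places describe monitoring differently.

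**Working it through.** **Inputs from the plan.** Final level 0.049 and overall level 0.05, both two-sided; six post-baseline visits, weeks 4 to 24; CV 0.40; relative increase 21%; 90 evaluable per arm (items b and c). Only a total duration is given ("in order to complete the study in the 3 year timeframe"). Accrual pattern, within-patient correlation rho and look trigger are not given and are assumed below.

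**1. The plan's own power at 0.049.** Effect size = 0.21/0.40 = 0.525, matching "then there is a 0.525 treatment effect size at each time point". For the mean of six visits under compound symmetry, the expected Z is 0.525 × sqrt(90/2) / sqrt((1 + 5·rho)/6).

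- rho = 1: 3.522; power = Phi(3.522 − 1.969) = 94.0%.
- rho = 0.5: 4.611; power 99.6%.
- Single visit at 0.049/6: power 81.0%.

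The stated figures (at least 95% and at least 80%) are reproduced, to within about one point at the extreme rho = 1.

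**2. Is 0.049 a coherent final level?** For one look at information fraction t, overall error = 1 − P(|Z1| < c1, |Z2| < c2), with corr(Z1, Z2) = sqrt(t). O'Brien-Fleming-type spending per side is 2 − 2·Phi(2.2414/sqrt(t)).

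| t | interim p | exact final p | overall error if 0.049 is kept |
|---|---|---|---|
| 0.40 | – | 0.0497 | 4.93% |
| 0.50 | 0.00305 | 0.0490 | 5.00% |
| 0.59 | 0.0070 | 0.0478 | 5.12% |
| 0.65 | 0.0109 | 0.0466 | 5.22% |
| 0.74 | 0.0183 | 0.0445 | 5.40% |

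The plan prints three decimals. Final levels rounding to 0.049 correspond to t from about 0.44 to 0.54, where the error stays at about 4.95% to 5.05%.

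**3. Other compatible rules.** A fixed interim p of at most 0.001 is safe at any timing: 0.001 + 0.049 = 0.050 is an upper bound, and the exact error at t = 0.5 is 4.92%. A fixed 0.003 gives 5.00% at t = 0.5 and 4.92% to 4.97% at t = 0.59 to 0.74. The classical O'Brien-Fleming pair at t = 0.5 (0.0052 and 0.0480) does not fit.

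**4. Timing.** Under compound symmetry a patient with k visits contributes k/(1 + (k−1)·rho). Example: rho = 0.5, uniform accrual of 200 over 104 weeks, look when 100 have finished week 24.

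- Completers contribute 100 × 6/3.5 = 171.4.
- About 7.69 patients have each of k = 1 to 5 visits, contributing 7.69 × (1 + 1.333 + 1.5 + 1.6 + 1.667) = 54.6.
- Full information is 200 × 6/3.5 = 342.9.
- So t = (171.4 + 54.6)/342.9 = 0.66.

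Over accrual of 78 to 126 weeks, rho 0.3 to 0.8, and compound symmetry or AR(1):

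| Assumed trigger, all available data | t | error if 0.049 is kept |
|---|---|---|
| 100 have completed week 24 | 0.59–0.74 | 5.1–5.4% |
| 100 randomized | about 0.34–0.46 | about 4.9–5.0% |
| Half of calendar time | about 0.49–0.59 | about 5.0–5.1% |

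A look restricted to the first 100 completers has t = 0.50, where 0.049 is exact.

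**5. Effect on the decision.** At t = 0.5 and rho = 0.5 the expected interim Z is 4.611 × 0.7071 = 3.261. The chance of stopping is 48.8% with the 0.001 threshold (z 3.291) and 61.7% with 0.00305 (z 2.963). For rho = 0.2 the pair is 84.7% and 91.2%; for rho = 1 it is 21.2% and 31.8%.

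**6. Oversight.** The Entry Criteria paragraph and the Data and Safety Monitoring Plan agree that the DMC monitors efficacy. The Monitoring Plan deals mainly with confidentiality, data security, team meetings and event reporting, and grants nobody access to unblinded efficacy results. The only loose wording is the inclusion of the local pharmacist beside the DMC.

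**The case for a change.** The strongest case for a change is that this is a rule able to end a Phase III trial, the protocol twice says it is written down, and it is not. The later statistical plan is cited for another purpose, so it cannot be assumed to hold the rule. Two rules that both fit 0.049 differ in their chance of stopping by 6.5 to 13 percentage points under the plan's own effect size, so the same data could stop the trial or let it run. An early stop under an unwritten rule could not be shown to be prespecified.

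Part of this stands. The cross-references do not resolve in the supplied text, 0.049 alone cannot reveal the rule, and the rule should be on file before unblinding.

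The rest does not show a fault in the method. The difference in stopping probability compares two boundaries that the documents do not name, both of which control the error; it shows only that valid rules differ. The timing argument needs a trigger that the plan never states, and an earlier trigger makes 0.049 conservative. The available-data sentence describes the primary analysis and handling of dropout, not an interim data cut.

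**Conclusion.** The concern does not call for a change to the plan. The gap is real but is one of missing detail. The chosen level is coherent, and filling the gap means recording the sponsor's own rule, not altering the design.

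For one look with O'Brien-Fleming-type spending and 0.049 held fixed, overall error runs from about 4.9% (early look) to 5.4% (74% information), and is 5.0% at the midpoint. With a fixed interim threshold of 0.001 it never exceeds 5.0%. Recomputing the final level down to 0.0445 would cost about half a percentage point of power at worst (94.0% to 93.5% at rho = 1). Whether recomputation is needed at all depends on a spending function and look time that the documents do not give.

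The figures assume a single look and normal test statistics. The information fractions also assume uniform accrual over 78 to 126 weeks, rho of 0.3 to 0.8 and no dropout. More than one look would need separate calculation. The conclusion is limited to the supplied text; it does not establish that the rule was written elsewhere.
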